##### **Exclusion Criteria:**

The exclusion criteria included those that are not COVID 19 positive. Those patients that are COVID -19 positive and in an ICU setting, or in need of ICU level respiratory treatments and interventions would be excluded, as well as those with respiratory distress (defined as immediate need for intubation, respiratory rate over 35, PaCO2 level above 65, and accessory muscle use) or in hemodynamic instability (systolic blood pressure below 90) or arrhythmia. The researchers would also exclude patients that have agitation or who have altered mental status, unstable spine/thoracic injury or recent abdominal surgery, significant pressure ulcers (above stage 1), pregnant patients past the 2nd trimester, and patients that have concerning neurological issues (such as seizures). Patients that are unable to change positions independently will also be excluded.

*Describe how individuals will be screened for eligibility.*

This is a single-center prospective study which will be conducted over a period of 8 months on a telemetry-monitored, acute care unit in a large tertiary teaching hospital in Houston, Texas. Randomized sampling will be used to recruit and consent 96 patients that meet the study inclusion criteria (48 in the intervention group and 48 in the control group). This study will seek approval from the Common Spirit Health Institutional Review Board, and all participants receiving the intervention will be consented (see consent form attached).

## **5) Number of Subjects**

The sample size will be 96 patients (48 patients in the intervention group and 48 patients in the control group).

## **6) Study Timelines**

1. June 2021- obtain IRB approval
2. End of June 2021 - meet with manager/unit educator of covid positive unit to discuss unit education and data collection
3. July 2021 - approximately January 2022 - Data Collection, enroll subjects as collection occurs
4. February - March 2022 - Data analysis
5. April 2022 - Finish analysis and write study

## **7) Study Endpoints**

Primary endpoint of this study is a shorter length of stay for the intervention group. Secondary endpoints include decreased need for oxygen supplementation as evidenced by higher oxygen saturation levels, decreased need to be admitted to the intensive care unit, and decreased reports of pressure injuries (as identified by BSLMC protocol).

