### 2) Objectives and Hypothesis(es)

The project goal is to investigate the efficacy of proning COVID-19 hypoxemic patients who are hospitalized at Baylor St. Luke's in an acute care, telemetry-monitored unit. The researchers will be using a systematic approach to educate patients and staff about patient self-proning, implementing self-proning every 2 hours, and monitoring escalation of oxygen levels, as well as length of the study period.

**Objectives:** This study is intended to explore the effects of proning on non-ventilated COVID-19 hypoxemic patients hospitalized in a telemetry-monitored, acute care unit. In addition, the hope is to delay intubation and/or escalation of respiratory interventions, while contributing to the growing body of knowledge related to COVID-19 treatment and care.

**Hypotheses:** The researchers expect to see an improvement in oxygen saturation levels as evidenced by no escalation of respiratory care (i.e. higher levels of oxygen needed, transfer to higher level of care), resulting in shorter lengths of stay for the intervention population.

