#### **4) Inclusion and Exclusion Criteria**

##### **Inclusion Criteria:**

The inclusion criteria for this research study are patients that have been confirmed COVID-19 positive on an acute-care, telemetry-monitored, non-ICU unit and are considered hypoxemic. Hypoxemic is defined as experiencing rising oxygen requirements as evidenced by increasing levels of supplemental oxygen (i.e. starting at 1-2 L nasal cannula and increasing oxygen need from that level, up to 6 L on nasal cannula.) The patient must also be conscious and oriented, as well as able to change positions independently (meaning that it would not take an increased amount of energy or effort to position independently. Subjects will be patients 18 years and older. If the patient is unable to speak, read, or write English, an alternative consent in their language will be utilized.

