## **8) Procedures Involved**

**Study Design:** This will be a prospective randomized cohort study in which data will be collected for over 14 days or until discharged or transferred to a lower level of care from the telemetry-monitored, acute care unit. Data collected on study participants will include the need for escalating respiratory care as well as length of stay in the acute care unit. Comparative analysis will be conducted with retrospective data collected from hospitalized patients (the control group) with a diagnosis of COVID-19 on a non-ICU acute care, telemetry-monitored unit that meets the hypoxemia criteria, but that will not receive the proning intervention. The data from the control group will be collected by a retrospective chart analysis after 14 days past their discharge date.

On a confirmed COVID-19 non-ICU acute care, telemetry-monitored unit, there will be two sets of patients: patients that will receive the intervention of proning plus standard of care, and patients that receive standard of care, but not the proning intervention. Confirmed COVID-19 positive patients are randomly assigned by bed control to a room upon admission to the unit. Patients will be randomized upon admission to the acute care, telemetry-monitored unit, and selected based

on inclusion criteria. The patients that will be prone will be identified by a door slot "slider" that is purple. Timing devices will be purchased and placed at the nurses' station, and checklists to indicate proning times will be placed inside the room with a patient identification sticker. The researchers will be following the proning protocol for acute care patients provided by CommonSpirit Health (CSH).

Patients will consent to participation (using an approved consent document from the CSH IRB), and an order for the proning protocol will be entered in the EMR by the physician. The patient will be educated about self-proning, and instructed to self-prone every 2 hours. The nursing staff will document patient position on the checklists every 2 hours.

1. Upon initiation of the initial proning, the patient will be monitored by the RN for adverse effects for 15 minutes (such as inability to tolerate position or signs of respiratory distress).

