2. If the patient tolerates the proning well, the procedure can continue and the RN will set the timer for 2 hours, enter the patient's oxygen saturation into the EMR, and document the position (prone or supine) on the checklist. O2 saturation will be documented at least every 4 hours per unit protocol.
3. The 2 hour timer will be reset each set of 2 hours by the nursing staff, and the intervention will continue until the end of the study period or until the patient is discharged or transferred from that unit.
4. The checklists will be placed in a binder at the nurses' station at the end of each shift and collected daily by a member of the research team.
5. This intervention for each "proned" patient will continue until either of the following occur: either the patient is discharged or transferred to a lower level of care from the acute care floor, or 14 days have passed.
6. A retrospective chart review will be completed by the research team to ascertain length of stay on the acute care, telemetry monitored unit, as well as the need for escalation of respiratory care. Escalation is defined by a need for oxygen requirements above 6 liters of oxygen on the nasal cannula.

*If the patient is assigned to the control group, that patient will receive the standard of care treatment designated by BSLMC policy per their condition on the COVID-19, acute care, telemetry-monitored unit.*

**Data Analysis:** Retrospective data analysis will be conducted by the research team with data collected from the electronic medical record as well as the checklists (oxygen saturation, demographics, proning protocol) for both the interventional and control group. See attached documents for consent/proning protocol documents.

This study will be a prospective cohort study in which data will be collected on subjects for the designated time period. Data will be collected from the electronic medical record as well as the checklists. Data collection will include basic patient demographics, specifically age and gender, height, weight and ethnicity. Clinical data to be collected include O2 saturation, respiratory support methods, proning duration/compliance, presence of hospital acquired pressure injuries,

and need to escalate care to ICU, including initiation of mechanical ventilation. The same data will be collected for the control group - except for proning duration/compliance as they will not receive this intervention.

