## **9) Data and Specimen Banking**

The data obtained from this study will be basic patient demographics, specifically age and gender, height, weight and ethnicity. The patient medical record number, name, and date of admission/discharge are included as PHI necessary to complete this study. Clinical data to be collected include O2 saturation, respiratory support methods, proning duration/compliance, presence of hospital acquired pressure injuries, and need to escalate care to ICU, including initiation of mechanical ventilation. The REDCap project IDs are 2817 and 3682 for reference.

Upon consent to the study, the patient's medical record number will be recorded as the principal identifier, and the above demographic data will be collected from the electronic medical record. This information will be coded to a personal ID generated by the researchers' REDCap software by the principal investigator or members of the research team. The clinical data obtained during and after the intervention will be recorded from the electronic medical record and also linked to the personal ID in the REDCap software.

The list linking the medical record number to the personal ID will only be handled by members of the research team and will be destroyed electronically upon completion of data collection - approximately 8 months after the initial start of the study. This is to allow for easy access of associated data as the researchers update the ID profiles. All of the members of the research team have completed CITI training, as well as financial conflict of interest records.

The researchers do not anticipate any incidental findings that would impact the outcome of this study or the care of the patient. If the patient started the study and then wished to have their data removed, the patient would communicate that to the nurse assigned, who would then call the principal investigator (number provided to the unit). The investigator would then delete the profile from REDCap and remove the medical record number from the study records.

Data collection will proceed as follows:

1. Every calendar day after the patient has been consented and the intervention is occurring, the nurse assigned to the patient will chart O2 saturation, any presence of hospital acquired pressure injuries, and need to escalate care. This data will be recorded in the electronic medical record, and members of the research team will daily update the REDCap profile with that data.

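### The oxygen-need secondary endpoint is read from saturation, which does not measure need when the oxygen given can change and differ between arms

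*Protocol*

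**What the plan says.** - **Endpoint (Section 7, Study Endpoints).** One secondary endpoint is "decreased need for oxygen supplementation as evidenced by higher oxygen saturation levels". Section 13 (Potential Benefits) again pairs lower oxygen need with higher recorded saturations.
- **Oxygen at entry (Section 4, Inclusion Criteria).** Eligibility is defined by a rising requirement: "starting at 1-2 L nasal cannula and increasing oxygen need from that level, up to 6 L on nasal cannula".
- **When saturation is read (Section 8, step 2).** In the proned arm, once the first proning is tolerated, the nurse will "enter the patient's oxygen saturation into the EMR, and document the position (prone or supine) on the checklist". More generally, "O2 saturation will be documented at least every 4 hours per unit protocol". Neither instruction mentions the oxygen flow at the reading.
- **Hypothesis (Section 2).** The investigators expect "improvement in oxygen saturation levels as evidenced by no escalation of respiratory care (i.e. higher levels of oxygen needed", with transfer to a higher level of care as the other example of escalation.
- **Escalation (Section 8).** The study design states: "Data collected on study participants will include the need for escalating respiratory care". Step 6 states: "Escalation is defined by a need for oxygen requirements above 6 liters of oxygen on the nasal cannula". Section 7 does not name escalation.
- **Data collected.** Sections 8 and 9 list saturation and methods of respiratory support among the clinical data. Section 8 says the same items are collected for controls, apart from proning duration and compliance. Under Section 9 the nurse each day "will chart O2 saturation, any presence of hospital acquired pressure injuries, and need to escalate care". Flow in litres is not named in any of these lists.

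**The concern.** Saturation in a patient on supplemental oxygen reflects both lung function and the oxygen being delivered. Oxygen need is the amount of support required. The two can move separately. A patient who goes from 6 L to 2 L at a steady saturation has a real fall in need, which the endpoint does not register. A patient whose saturation rises after going from 2 L to 6 L has a rise in need, which the endpoint counts as benefit.

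For the comparison between arms, what matters is the oxygen given after entry. If proning works and proned patients come to receive less oxygen than controls, the saturation difference shrinks and the endpoint can show no benefit. If proned patients receive more oxygen, it can show a benefit that proning did not produce. This is the only secondary endpoint on oxygenation, the effect the study sets out to examine.

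The protocol is also inconsistent about what evidences what. Section 7 infers need from saturation, Section 2 infers saturation from the absence of escalation, and Section 8 measures escalation in litres.

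**Working it through.** **No figure of the plan to reproduce.** The only design calculation is for time to discharge (48 per group, 80% power, Section 10). The endpoint definition does not depend on it. The documents give no saturation mean, SD, flow distribution or escalation rate, so apart from the 48 per arm every input below is assumed.

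**Step 1: the sections side by side.**

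| Protocol section | Inference or measure |
|---|---|
| 2, hypothesis | no escalation → better saturation |
| 7, endpoint | higher saturation → lower need |
| 8, step 6 | escalation = above 6 L by nasal cannula |
| 8, step 2 | saturation at the start of proning and at least every 4 hours; no flow condition |

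The first two arrows run in opposite directions. The third row measures need directly, and Section 7 does not use it.

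**Step 2: how far masking could go.** Assume proning truly adds 2 saturation points at equal oxygen, with SD 2.5 (range 2 to 3), 48 per arm and a two-sided 5% test. Let t be the share of the gap closed by extra oxygen in controls.

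- Standard error = SD × √(2/48); for SD 2.5 this is 2.5 × 0.2041 = 0.510.
- z = 2(1 − t) / SE, and P(significantly favours proning) = Φ(z − 1.96).
- For SD 2.5, t = 0: z = 3.92, P = Φ(1.96) = 0.975.
- For SD 2.5, t = 0.5: z = 1.96, P = Φ(0) = 0.500.

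| SD | t = 0 | t = 0.5 | t = 1 |
|---|---|---|---|
| 2 | 0.998 | 0.688 | 0.025 |
| 2.5 | 0.975 | 0.500 | 0.025 |
| 3 | 0.904 | 0.372 | 0.025 |

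The last column holds by construction: with no gap left, only the false-positive rate in that direction remains.

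**Step 3: a second illustration, with oxygen adjusted to a saturation target.** Assume saturation without oxygen has mean 86 and SD 2, each litre adds 2 points, and proning adds 2 points at any flow. With flow held at 3 L in everyone, simulated arms differ by 2.0 points. With flow adjusted in whole litres (maximum 6 L) to a target of 92 or 94, mean saturation differs by 0.00 or 0.04 points, while mean flow is lower in the proned arm by 1.00 or 0.97 L. The benefit has moved from saturation to flow. The targets serve only the simulation; the protocol states none.

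**Step 4: what the alternatives could detect with 48 per arm.**

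- Support level: (1.960 + 0.842) × √(2/48) = 0.572 SD at 80% power. For an assumed SD of 1, 1.5 or 2 L this is 0.57, 0.86 or 1.14 L.
- Escalation above 6 L: by the two-sided normal approximation, 80% power requires falls from 40% to 14.8%, from 30% to 7.9%, or from 20% to 2.2% (control rates assumed). Power at these pairs depends on the test: about 73% to 74% by Fisher's exact test, and 81% to 88% by the pooled z test when its power is computed exactly. In the last pair only about one event is expected in the proned arm (48 × 0.022 = 1.06).

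**The case against.** **Entry flows need not bias the comparison.** A reader might infer that the range of flows at entry distorts the result. Under the random allocation the protocol states, entry flows differ by chance and mainly add noise. This stands. Systematic error needs a difference between arms in the oxygen given after entry.

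**Readings are not timed only by the clock.** A reader of the 4-hour rule alone might think so, but step 2 also ties a reading to the start of proning. This stands too, but it changes nothing for this point, because neither reading carries a flow condition.

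**Direct data on support are already collected.** A reader might infer from the endpoint that the study gathers nothing better than saturation. It does: methods of respiratory support are recorded in both arms, and chart review ascertains escalation. That makes the repair cheap. It does not repair the endpoint, because Section 7 uses neither.

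**Documents not at hand may set reading conditions.** The proning protocol, the unit protocol and hospital policy are cited but not shown, and the protocol contains no rule for adjusting oxygen. How much masking would occur is therefore unknown. But the endpoint does not refer to those documents, and the one unit rule the protocol cites for readings is a time interval.

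**Section 2 is a loosely worded hypothesis, and the list in Section 7 may not be exhaustive.** Fair. The reversal in Section 2 is an inconsistency to align, not a second faulty endpoint, and the absence of escalation from Section 7 is a matter of clarity.

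**Conclusion.** The point holds for this secondary endpoint. Section 7 fixes a definition that does not measure the quantity it names, so this is not a detail left to an analysis plan. Followed as written, the endpoint can miss a real fall in oxygen need or credit added oxygen as benefit, provided that the oxygen given after entry differs between arms. The rising flows in the eligibility criteria make that plausible; the documents do not show that it will happen.

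The size cannot be derived from the documents. Under the assumptions shown, the chance of a significant result for proning falls from 97.5% (90% to 99.8% over SD 3 to 2) at equal oxygen to 50% (37% to 69%) when half the gap is closed. Only masking is quantified; false credit for added oxygen is not. A reader might infer that the saturation result is certain to be biased, or that the trial's main conclusion is at risk. Neither follows: the amount of bias is unknown, and the primary endpoint, time to discharge, is unaffected.

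**What to change.** 1. **Section 7.** Define the oxygen-need endpoint on oxygen support itself. Use the methods of respiratory support already collected in both arms, with flow in litres abstracted from the chart if it is not already captured, or the protocol's own escalation above 6 L (Section 8, step 6), or both. Either choice removes the defect.
2. **Saturation.** Report it separately and descriptively, with the oxygen given at the reading, and not as evidence of need.
3. **Section 2.** Reword the hypothesis so that Sections 2, 7 and 8 agree on what is measured and what it shows. State whether transfer to a higher level of care, which Section 2 counts as escalation, belongs to the escalation endpoint, since ICU admission is already a separate secondary endpoint.

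**Cost.** Mostly wording, plus possibly one added chart field in both arms. Escalation already comes from the planned chart review.

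**Downsides.** Support level is set by staff who can see the arm (the purple door marker in Section 8), so it is open to influence by knowledge of allocation. Escalation with 48 per arm can detect only large differences and is better read as supportive. No change to treatment or to the giving of oxygen is implied.

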## **8) Procedures Involved**

**Study Design:** This will be a prospective randomized cohort study in which data will be collected for over 14 days or until discharged or transferred to a lower level of care from the telemetry-monitored, acute care unit. Data collected on study participants will include the need for escalating respiratory care as well as length of stay in the acute care unit. Comparative analysis will be conducted with retrospective data collected from hospitalized patients (the control group) with a diagnosis of COVID-19 on a non-ICU acute care, telemetry-monitored unit that meets the hypoxemia criteria, but that will not receive the proning intervention. The data from the control group will be collected by a retrospective chart analysis after 14 days past their discharge date.

On a confirmed COVID-19 non-ICU acute care, telemetry-monitored unit, there will be two sets of patients: patients that will receive the intervention of proning plus standard of care, and patients that receive standard of care, but not the proning intervention. Confirmed COVID-19 positive patients are randomly assigned by bed control to a room upon admission to the unit. Patients will be randomized upon admission to the acute care, telemetry-monitored unit, and selected based

on inclusion criteria. The patients that will be prone will be identified by a door slot "slider" that is purple. Timing devices will be purchased and placed at the nurses' station, and checklists to indicate proning times will be placed inside the room with a patient identification sticker. The researchers will be following the proning protocol for acute care patients provided by CommonSpirit Health (CSH).

Patients will consent to participation (using an approved consent document from the CSH IRB), and an order for the proning protocol will be entered in the EMR by the physician. The patient will be educated about self-proning, and instructed to self-prone every 2 hours. The nursing staff will document patient position on the checklists every 2 hours.

1. Upon initiation of the initial proning, the patient will be monitored by the RN for adverse effects for 15 minutes (such as inability to tolerate position or signs of respiratory distress).
2. If the patient tolerates the proning well, the procedure can continue and the RN will set the timer for 2 hours, enter the patient's oxygen saturation into the EMR, and document the position (prone or supine) on the checklist. O2 saturation will be documented at least every 4 hours per unit protocol.
3. The 2 hour timer will be reset each set of 2 hours by the nursing staff, and the intervention will continue until the end of the study period or until the patient is discharged or transferred from that unit.
4. The checklists will be placed in a binder at the nurses' station at the end of each shift and collected daily by a member of the research team.
5. This intervention for each "proned" patient will continue until either of the following occur: either the patient is discharged or transferred to a lower level of care from the acute care floor, or 14 days have passed.
6. A retrospective chart review will be completed by the research team to ascertain length of stay on the acute care, telemetry monitored unit, as well as the need for escalation of respiratory care. Escalation is defined by a need for oxygen requirements above 6 liters of oxygen on the nasal cannula.

*If the patient is assigned to the control group, that patient will receive the standard of care treatment designated by BSLMC policy per their condition on the COVID-19, acute care, telemetry-monitored unit.*

**Data Analysis:** Retrospective data analysis will be conducted by the research team with data collected from the electronic medical record as well as the checklists (oxygen saturation, demographics, proning protocol) for both the interventional and control group. See attached documents for consent/proning protocol documents.

This study will be a prospective cohort study in which data will be collected on subjects for the designated time period. Data will be collected from the electronic medical record as well as the checklists. Data collection will include basic patient demographics, specifically age and gender, height, weight and ethnicity. Clinical data to be collected include O2 saturation, respiratory support methods, proning duration/compliance, presence of hospital acquired pressure injuries,

and need to escalate care to ICU, including initiation of mechanical ventilation. The same data will be collected for the control group - except for proning duration/compliance as they will not receive this intervention.

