## **10) Data Analysis Plan**

Retrospective data analysis will be conducted by the research team with data collected from the electronic medical record as well as the checklists (oxygen saturation, demographics, proning protocol) for both the interventional and control group. See attached documents for consent/proning protocol documents.

This study will be a randomized controlled trial. The primary outcome will be time (days) until discharge from the acute care unit to home or lower level of care (e.g., long-term care), and the primary hypothesis test will compare time-to-discharge between "prone" and "not prone" treatment arms.

A sample size of 48 patients per group (N=96) will provide 80% power to detect a 50% decline in time-to-discharge using a log-rank test.

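### Data collection is written to stop at the primary-outcome event, so later ICU admission and ventilation are not planned to be counted, or might be counted only in controls

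*Protocol*

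**What the plan says.** **Window.** Section 8, Study Design: "data will be collected for over 14 days or until discharged or transferred to a lower level of care".

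**Primary outcome.** Section 10: "time (days) until discharge from the acute care unit to home or lower level of care". The event that scores the primary outcome is also the one that closes data collection.

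**Secondary outcomes.** Section 7 lists "decreased need to be admitted to the intensive care unit, and decreased reports of pressure injuries" with no time horizon. Sections 8 and 9 add mechanical ventilation to the data collected.

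**Daily charting.** Section 9 has the nurse record saturation, pressure injury and need to escalate "Every calendar day after the patient has been consented and the intervention is occurring". Section 8, step 5, continues proning until "either the patient is discharged or transferred to a lower level of care from the acute care floor, or 14 days have passed". Step 5 governs how long proning lasts, not how long outcomes are observed. It matters here only because section 9 links charting to the intervention.

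**Chart review.** Section 8, step 6, plans a retrospective review "to ascertain length of stay on the acute care, telemetry monitored unit, as well as the need for escalation of respiratory care", with no horizon after the unit.

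**Text pointing the other way.** Section 9: "The clinical data obtained during and after the intervention will be recorded from the electronic medical record". For controls only, section 8 says the data will be "collected by a retrospective chart analysis after 14 days past their discharge date".

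**The concern.** ICU admission and ventilation accumulate with time observed. If observation ends when the patient leaves for home or a lower level of care, length of stay sets the time at risk. A patient stepped down on day 3 who enters ICU on day 5 would count as an early discharge with no ICU admission.

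An arm that leaves sooner, for whatever reason, then tends to show fewer ICU admissions. Staff know the assignment, because section 8 marks the doors of proned patients, so the timing of discharge could be influenced by it. A reader of a length-of-stay result will want to know whether earlier departure was followed by deterioration, and a count that stops at departure cannot show this.

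The arms might also be observed differently. If the later reading of control charts picked up ICU admissions after the unit while data on proned patients stopped at departure, the asymmetry would again favour proning.

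**Working it through.** **Reading the text.** The explicit window in section 8 and the charting rule in section 9 both stop at departure. The two sentences pointing the other way foresee some later data, but neither says which events or up to when. The control sentence says when charts are read, not which period they cover. So later events are not planned to be counted, or might be counted only in controls.

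**Inputs for size.** The protocol gives no ICU rate or median stay, so there is no plan figure on this point to reproduce. From the protocol: a 50% decline in time to discharge, 48 patients per arm, and a 14-day cap. Assumed: exponential times; median stays of 8 days (control) and 4 days (prone); an ICU hazard on the unit of h = 0.03 per day in both arms; and an ICU hazard after leaving of r, varied from 0 to 0.03 per day.

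**Discharge hazards.** d = ln 2 / 8 = 0.0866 (control) and d = ln 2 / 4 = 0.1733 (prone).

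**Counted on the unit only.** Risk = h/(h+d) × (1 − exp(−14(h+d))).
- Control: 0.2572 × (1 − 0.1953) = 0.207
- Prone: 0.1476 × (1 − 0.0581) = 0.139
- Ratio: 0.139 / 0.207 = 0.67

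**All ICU admissions to day 14.** Add the integral from 0 to 14 of d·exp(−(h+d)t)·(1 − exp(−r(14−t))) dt.

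| r per day | Control | Prone | Full ratio | Counted ratio | Share missed, control / prone |
|---|---|---|---|---|---|
| 0 | 20.7% | 13.9% | 0.67 | 0.67 | 0 / 0 |
| 0.0075 | 24.5% | 19.6% | 0.80 | 0.67 | 16% / 29% |
| 0.015 | 28.0% | 24.9% | 0.89 | 0.67 | 26% / 44% |
| 0.03 | 34.3% | 34.3% | 1.00 | 0.67 | 40% / 59% |

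The uncounted admissions per 48 patients (control and prone) are about 1.8 and 2.8, then 3.5 and 5.3, then 6.5 and 9.8 for the three non-zero values of r.

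**If later events were captured in controls only.** The prone count stays at 13.9% and the control count rises to the full figure. The ratios are 13.9/24.5 = 0.57, 13.9/28.0 = 0.50 and 13.9/34.3 = 0.41, each further below the full ratio than 0.67 is.

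**Sensitivity to the assumed rates.** Set the true day-14 ICU risk at 20% in both arms, with unchanged risk after leaving and medians of 8 and 4 days. Counting on the unit only gives 11.8% and 7.8%, a ratio of 0.66 where the truth is 1.00. Over control medians of 6 to 10 days and day-14 ICU risks of 10% to 28%, that ratio runs from 0.61 to 0.71.

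**The case against.** **Later ICU admissions are not ruled out.** A reader might infer from section 8 that they can never be counted. The documents do not support that. Section 9 foresees data after the intervention, control charts are read 14 days or more after discharge, and the step 6 review has no stated stop. What stands is that the window after the unit is undefined and may differ between arms.

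**The whole one-third reduction need not be spurious.** That reading holds only if patients judged fit to leave keep the same ICU hazard as those still on the unit. At r = 0.0075 the full ratio is itself 0.80, and the arms differ by about one uncounted patient. Even the counted contrast, roughly 10 against 7 of 48, is far from significant (Fisher p about 0.59). The illustration also presumes the full 50% shortening of stay. All of this stands, and the size must be stated as conditional.

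**Pressure injury is a weaker case.** Sections 8 and 9 collect only hospital-acquired injuries. After discharge home there is no hospital exposure, so fewer injuries after a shorter stay would be largely real. The point reaches only injuries acquired after step-down within the hospital or on readmission. Oxygen saturation is a level rather than a count and is not mechanically lowered.

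**ICU transfer from the unit is still captured.** ICU is not a lower level of care, so deterioration on the unit inside the window is recorded. Nor does section 7 give these endpoints the task of checking for premature discharge. Both are true. The second limits how strongly the harm can be put, but not the dependence of the count on length of stay.

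**An analysis plan may settle horizons and competing events.** It may, but it cannot analyse events that were not collected, and the collection window is fixed in the protocol.

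**Conclusion.** The point holds in a limited form. The protocol's stated window closes at the primary-outcome event, and its other sentences do not define what is collected afterwards. As written, ICU admission and mechanical ventilation after step-down or discharge are not planned to be counted, or might be counted only in controls. Either way the count tends to favour the arm that leaves sooner.

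Under the assumed stays and unit hazard, the counted ratio of 0.67 stands against a full day-14 ratio of 0.80, 0.89 or 1.00, depending on risk after the unit. With no such risk there is no distortion. Those inputs are assumptions; only the 50% reduction, the arm size and the 14-day cap come from the protocol. The primary log-rank comparison is not affected, but these endpoints would be a poor guide to what followed earlier discharge.

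**What to change.** Reconcile the collection window in section 8 with the charting and recording statements in section 9, and state one rule for both arms:

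- Define ICU admission and mechanical ventilation as occurrence by day 14 from assignment.
- Ascertain them identically in both arms from the hospital's electronic record, whether or not the patient has left the unit.
- Count hospital-acquired pressure injury over the same 14 days during any stay in the hospital, including after step-down or on readmission.
- Report beside the primary result how many patients counted as discharged were in ICU or readmitted by day 14.

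The cost is a short amendment and a small extra chart look-up. The team already records the medical record number and plans a retrospective chart review. Admissions to other hospitals would remain unseen, and the report should say so.
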